COMIRB Protocol

COLORADO MULTIPLE INSTITUTIONAL REVIEW BOARD [name] [contact] [contact]

Protocol #:	20-2772
Project Title:	Discontinuation of Disease Modifying Therapies (DMTs) in Multiple Sclerosis (MS): Extension of the DISCOMS Study
Principal Investigator:	[name]
Version Date:	12Aug2021

I. Hypotheses and Specific Aims:

Main hypothesis: The DISCOntinuation of disease modifying therapies (DMTs) in Multiple Sclerosis (MS-DISCOMS) study is a maximum two-year, randomized controlled clinical trial (RCT) assessing whether relatively older (55+), stable (no relapse for 5+ years, no new magnetic resonance imaging abnormalities of the brain or spine for 3+ years) MS patients who discontinue their DMT have no greater recurrence of disease activity compared to those who continue use of their DMT. We propose an extension of this trial in a 100-person subset of those from the original study who remain in their original drug assignment group at the end of the primary DISCOMS trial in order to continue to assess the duration of follow-up to more fully answer the question of the duration of safe withdrawal if that is the case. To date, the DSMB has not stopped the study, and the final participants have not completed the trial as yet. Thus, we have no new information on the equipoise of the original hypothesis. The **Main Hypothesis of this extension trial** is that among those who have successfully discontinued their DMT as part of the DISCOMS trial (i.e. did not have a new MS relapse or brain MRI lesion) and remain off DMT after DISCOMS are at no greater risk of new or worsened MS disease activity compared to those who successfully continued their DMT as part of DISCOMS and remain on DMT, each assessed at least one year after termination of the primary DISCOMS study.

Specific Aims:

In MS patients who participated in the primary DISCOMS trial, successfully completed a minimum of 18 months of the two year primary DISCOMS study and remained in their original assignment group (i.e. either have discontinued or continued their DMT or another DMT), we will compare clinically significant and patient-relevant outcomes in those who have persistently discontinued vs persistently continued DMTs to determine if:

- 1. Risk of new relapses or brain MRI lesions is no worse in those persistently discontinuing
- 2. Risk of disability progression (by the Extended Disability Status Scale EDSS) is no worse in those persistently discontinuing

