- 3. Cognition, quality of life and other patient-reported outcomes (PROs) are no worse in those persistently discontinuing

II. Background, Preliminary Studies, and Significance:

Multiple sclerosis (MS) is a debilitating neurologic disorder that is now estimated to afflict over 700,000 and perhaps over 900,000 people in the US.¹ At onset, it most often affects young people in the prime of their lives, with a median age of onset around 30,² but 46% of adults in the US with MS are 55 or older.¹ The average lifespan is diminished by 7-14 years.³⁻⁵ Most individuals with MS struggle with the condition for many decades. MS is a presumptive autoimmune condition affecting the central nervous system (CNS), including the brain, spinal cord and optic nerves.⁶ Pathologically it is associated with demyelination, axonal loss and neurodegeneration of both the white and gray matter of the CNS.⁶⁻⁸ On magnetic resonance imaging (MRI), lesions may similarly be seen in these locations. While formal diagnostic criteria have evolved over time, the concept of development and manifestation of CNS lesions disseminated in space (within the CNS) and over time, with other causes ruled out, remains the hallmark of MS diagnosis.⁹

MS is one of the most disabling conditions in the US and other Western countries. Patients, their families and society are affected with loss of neurological function, loss of employment, loss of social interaction, and high financial costs.^{1,10-12} While a small percentage of MS patients have a relatively modest or benign course, the vast majority of untreated MS patients develop measurable disability over time, with about half of untreated patients using a cane or other assistive device within 15 years of symptoms onset.¹³ Those using a cane are about 75% likely to be unemployed due to MS and will endure annual medical costs about 10 times higher than those with no or minimal disability.¹⁴

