a. Aim #1: Proposed Data Analysis: We will perform an extension of the primary DISCOMS study, that being the time to failure defined as a protocol-defined disease event with each treatment group extending the understanding of the durability of the assigned treatment arm beyond the original DISCOMS follow-up period. A countable event will be a new protocol-defined relapse, and/or a new brain MRI lesion. We will estimate the long-term differences between the two treatment arms. Further by linking the time to event within the 100 participants with the original DISCOMS event free survival estimates, we can further evaluate the null hypothesis of inferiority with the proportion of disease events for the discontinue group being 0.08 proportion worse (our original noninferiority margin) at later time points of follow-up than the proportion for the continue group under the alternative that the two rates are equal. Because of the expected small numbers of events, we will use Kaplan-Meier estimates of the differences to obtain a confidence interval for comparing the proportions with individuals counted at their respective event times or censored based on their last known status. If the upper bound of the 95% confidence interval for the difference between the groups is less than 0.08, then we can reject inferiority and rule out discontinuation increasing the disease event proportion by 0.08 or greater. Our primary goal here is to estimate these differences given the relatively small sample size included, but we will calculate these values using the data obtained. In the unlikely event the proportions are relatively large, we will also calculate estimates and confidence intervals for relative risks. Larger numbers of events would permit the fitting of more complex models, but to date we know that the majority have not failed although their assignments are not known to us.

b. Aim #2: Proposed Data Analysis: We will calculate estimates and confidence intervals, using exact methods as necessary, for the proportion of disease events in both the discontinue and continue groups after this extension

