c. Aim #3: Proposed Data Analysis: Descriptive statistics on patient demographics, PDDS, MSIS, performance and NeuroQOL short form scales, and all other PROs will be prepared for treatment group by occurrence of disease event, and qualitatively compared. Pre-Post changes, from baseline and from the entry into the Extension study (with the randomization maintained) will be compared between treatment groups. Change scores will be used for continuous and metric outcomes, and the treatment groups will be compared with two sample T-tests, or Wilicoxon tests if necessary. Binary outcomes, such as dichotomized changes in EDSS and other scales, will be tested with chi-square and proportion tests, or exact methods as necessary. MSIS will be divided into patients with greater or less than a change of 7.5 (considered a significant change). Correlations between continuous scales will be examined, and compared between treatment groups. Events will also be compared to non-events, and combinations of (event outcome) will be tested for differences, using similar methods, in the unlikely situation there are enough events to permit meaningful statistical analysis (>= 10 samples for an analysis group). Multiple groups can be tested with ANOVA methods for continuous outcomes, and with chi-square tests and logistic regression for binary outcomes.

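### Aim 3 asks whether outcomes are no worse, but its planned tests look for a difference and set no confidence interval or margin

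*Combined protocol and SAP*

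**What the plan says.** - **Section I, Specific Aims.** The groups are compared in order to determine three things. The second is: "Risk of disability progression (by the Extended Disability Status Scale EDSS) is no worse in those persistently discontinuing". The third is whether cognition, quality of life and other patient-reported outcomes "are no worse in those persistently discontinuing".
- **Section III.F, c. Aim #3.** For change scores, "the treatment groups will be compared with two sample T-tests, or Wilicoxon tests if necessary". For the rest, "Binary outcomes, such as dichotomized changes in EDSS and other scales, will be tested with chi-square and proportion tests, or exact methods as necessary". No significance level, sidedness, SD, target difference, margin or confidence interval is given. The only numerical threshold for a scale is a cut applied to individual patients: "MSIS will be divided into patients with greater or less than a change of 7.5".
- **Section III.F, a. Aim #1.** This is the only aim with a non-inferiority rule: the upper 95% confidence bound for the difference in event proportions must lie below 0.08.
- **Section III.F, b. Aim #2.** Proportions in each group are estimated with confidence intervals, and the aim is called mostly descriptive.
- **Section III.F, text after the sample size.** For Aims 2 and 3, differences in change scores are to be estimated to describe the longer follow-up.
- **Section III.E.** The plan concedes that the extension lacks the power to address non-inferiority.

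**The concern.** 'No worse' is a one-directional claim about the largest harm still compatible with the data. It can be answered only by seeing how far a confidence interval reaches in the harmful direction. A test of equality answers something else: failing to reject it may mean that the groups are alike, or that the sample is too small or the scale too noisy to tell. The authors use the interval logic for Aim 1 but not for Aim 3.

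Section III.G says the results should inform patients, physicians, insurers and regulators about continuing treatment. If a non-significant comparison of cognition, quality of life or EDSS change were taken as reassurance, that reassurance would have no support. The plan does not say which text governs, the aims or the descriptive language, or what a non-significant test permits.

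**Working it through.** **1. The plan's own figure.** The sample size paragraph gives a one-sided Fisher exact p of 0.036 for 10/50 against 3/50 failures. Recomputed: 0.0357 one-sided (0.071 two-sided), so it reproduces. It concerns failures by arm. No sample size or power is given for Aims 2 or 3.

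**2. Inputs for Aim 3.**
- From the plan: about 50 per arm (sample size paragraph); 100 finishers (opening of III.F); a possible 59:41 split if the early pattern holds (III.C).
- Assumed: two-sided 5% level, and true worsening of 0.2 to 0.5 SD of the change score. Working in SD units avoids assuming an SD for each scale.

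**3. How often a real worsening would be non-significant.** Two-sample t-test with noncentrality d × √(n₁n₂/(n₁+n₂)). With 50 per arm, √(2500/100) = 5, so d = 0.3 gives 1.5, against a critical value of 1.984 on 98 df.

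| True worsening | Power, 50:50 | Non-significant, 50:50 | Power, 59:41 |
|---|---|---|---|
| 0.2 SD | 17% | 83% | 16% |
| 0.3 SD | 32% | 68% | 31% |
| 0.4 SD | 51% | 49% | 50% |
| 0.5 SD | 70% | 30% | 68% |

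**4. What the interval would show.** The 95% half-width is 1.984 × √(2/50) = 0.397 SD (0.403 SD at 59:41). An observed difference of exactly zero would still leave a worsening of about 0.40 SD inside the interval. An observed worsening just short of significance, about 0.397 SD, would have an upper limit near 0.397 + 0.397 = 0.79 SD. Both results are non-significant, yet they say very different things about harm. The p-value alone does not separate them; the interval does.

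**5. A binary outcome.** Assume 14% against 6%. The 6% is taken from the sample size example, and the excess of 0.08 is borrowed from Aim 1 for illustration only. Exact Fisher power at 50 per arm is 15% two-sided and 26% one-sided, so this excess would be missed in about 74% to 85% of trials.

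**6. Would formal non-inferiority be feasible instead?** With one-sided 2.5%, 80% power and a true difference of zero, n per arm = 2 × (1.960 + 0.842)² / margin², with the margin in SD units. Assumed margins of 0.2, 0.3, 0.4 and 0.5 SD need 393, 175, 99 and 63 per arm. At 50 per arm the power is 17%, 32%, 52% and 70%. This agrees with the concession in III.E and points to estimation as the realistic aim.

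**The case against.** The strongest reply is that the plan has largely disclaimed this already. Section III.E admits that non-inferiority cannot be addressed and warns that unblinded patients may bias the patient-reported outcomes. Aim #2 has confidence intervals and is called mostly descriptive. The closing analysis text promises estimates of differences for Aims 2 and 3, and Aim #3 itself opens with descriptive statistics and qualitative comparison.

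Much of that stands:
- A reader might infer that the plan will declare 'no worse' from a non-significant p-value. No section says so.
- A reader might infer that a p-value is the only route to a conclusion on Aim 3. It is not, because estimates of differences are also planned.
- A reader might infer that the Aim 2 analysis is faulty. Its own section is already estimation. What does not fit is the aim's wording and the listing of dichotomised EDSS change among the outcomes tested under Aim #3.

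The disclaimers do not close the gap. The aims still promise a determination, Aim #3 specifies only tests of difference as its inferential method, and no interval is attached to the estimated differences in change scores.

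**Conclusion.** The point holds as a mismatch between question and method: Aim 3 poses a 'no worse' question that its stated tests cannot answer, and Aim 2 is worded more strongly than its descriptive analysis supports. With about 50 per arm, a true worsening of 0.3 SD would be non-significant about 68% of the time (69% at 59:41). This rests on an assumed effect size and a two-sided 5% level, since the documents give neither.

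Two stronger readings are not supported. One is that non-significance is likely whatever the harm. For a true mean difference of 7.5 MSIS-29 points, the t-test would be non-significant in 4%, 13%, 30% or 54% of trials at assumed SDs of 10, 12, 15 or 20. It becomes more likely than not only at the largest SD. The other is that 7.5 supplies a ready-made margin for MSIS-29. In the plan it divides individual patients. A difference between group means just under 7.5 could coexist with many more discontinuers crossing that cut, so using it as a between-group margin would be an invention, and possibly a lenient one.

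The point is minor: the aims are secondary, the limits on power are partly acknowledged, and the remedy is nearly free.

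**What to change.** 1. In Specific Aims, reword Aim 3 as estimating the difference between persistent discontinuers and continuers in change in cognition, quality of life and other patient-reported outcomes. Reword Aim 2 in the same way, to match its descriptive analysis.
2. In III.F, c. Aim #3, make the between-group difference in each change score or proportion, with its 95% confidence interval, the main result. Include dichotomised EDSS change. Any test is supplementary.
3. Add one sentence: a non-significant test will not be reported as showing that discontinuers are no worse.
4. Keep the MSIS-29 cut of 7.5 for classifying patients only, not as a between-group margin.

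No participants, visits or data are added; the intervals come from data already collected. The cost is that the permitted conclusions for Aims 2 and 3 become more modest.

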- During the primary DISCOMS study, no evidence of recent new inflammatory disease activity (inactive by the Lublin criteria¹⁶). Pseudorelapses due to infection, fever, or other stressors as deemed by the local PI will NOT be excluded. Those who have already successfully completed the primary DISCOMS study without having a new relapse or MRI scan change, but who have a relapse or scan change AFTER ending participation in DISCOMS but before entering the extension ARE eligible and will be recruited, i.e. we do not wish to undercount new activity that occurs after exiting DISCOMS.
- Provides informed consent to continue in the extension trial.
- Willing to follow the protocol.

• Able to undergo a brain MRI without anesthesia, as part of routine care (i.e. paid for by their insurance). * Continuously will be defined as no less than 75% of all prescribed doses, with no time of greater than four weeks from last intended dose to have missed a dose (8 weeks for natalizumab, i.e. one missed dose).

Exclusion criteria:

- During original DISCOMS trial participant was randomized to the discontinue group, but then either restarted their DMT during the trial (study-defined 'treatment withdrawal), or wishes to restart their DMT after completing original DISCOMS study. Conversely, also excluded are those who completed the primary trial in the continue group and then discontinued, or wishes to discontinue, after completion of the primary study.
- Any MS relapse or new MRI scan lesion (3 mm or larger) during the primary DISCOMS trial, with relapse determined by the blinded examiner and MRI lesion determined by the blinded MRI reader.
- Significant (as defined by the PI) intolerance of presently-used DMT, if taking a DMT
- The following must **not** have occurred during the original DISCO MS study or since completing the study:
 - Use of any non-FDA-approved DMT
 - More than two courses of acute, systemic (IV or oral). Course is defined as three or more days continuously, and not to exceed 14 days. No use of chronic, systemic steroids, defined as 15 or more days. Any use of steroids to treat MS relapse, possible relapse, or pseudo-relapse is excluded. Inhaled or topical steroids for non-MS are not exclusionary.
 - Use of alemtuzumab, mitoxantrone, cyclophosphamide, methotrexate, cyclosporine, rituximab, or cladribine.
 - \circ $\,$ Use of any experimental agent used as a DMT for MS $\,$
 - Cancers other than basal cell skin cancers

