This will be a non-randomized, rater-blinded pragmatic trial, which is an extension of the randomized discontinuation trial (RDT)⁸², DISCOMS. While RDTs have been done in cancer^{83,84} and rheumatoid arthritis patients,⁶⁶ the original DISCOMS protocol was the first such study in MS. For this protocol, a subset of 100 subjects of the original 260 enrolled will be followed. Study sites will be limited to the top 10 recruiting sites across the United States from the DISCOMS study due to financial and cost-effectiveness issues. Those sites will have participants who have completed 18-24 months of the primary study. In practice, the vast majority, if not all, will have completed 24 months. We will explicitly include any who have completed, including those who already have exceeded 12 additional months after completion of the primary trial. Individuals who have successfully completed (retained original drug assignment and did not meet the primary endpoint of DISCOMS) the primary DISCOMS trial and are willing to retain their original drug assignment after completion and for an additional 12 months will be offered entry into the extension. The only exception to that will be individuals who continued the original drug assignment during and after the primary trial, up to 24 months, but who then had a relapse, new MRI lesion, or other MS-related reason between months 24 and 36 which resulted in their change of medication assignment. These individuals can and should be included, and counted as "failing" during the extension trial completing the Kaplan-Meier event free survival curve critical to the original hypothesis. A total of up to 100 patients will be consented and enter the extension trial, regardless of assignment, on a first come first serve basis to avoid selection biases to the extent possible. The intent is to take the first 100 who fulfill criteria and agree to participate. The plan is for a 50/50 distribution, but there may not be exactly 50 in each group. As of December 15, 2020, 123 had completed participation of the primary 24-month study, and information as to DMT use plans after finishing 2-years participation in DISCOMS was available for 84/123, 42 in each group (see Table 1 below). Notably, in the Discontinue group, 86% remained off DMT while only 60% in the Continue group plan to remain on a DMT (23/42 on the same DMT, two switching to an alternative). Overall 73% remained in the primary assignment grouping. If these ratios stay consistent as more finish DISCOMS, discontinuers will account for roughly 59% of the total enrolled in the extension trial. Also, of the 123 completers, 49 have also gone at least an additional 12 months since completion of DISCOMS, and they will be offered entry into the extension trial, should they otherwise fulfill criteria. There will be no placebo and no sham treatment. (Please see the statistics section the extension ns for power analyses discussions).

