
Table 1. Use of Disease Modifying Therapy after two years of participation in DISCOMS.

	Stop my DMT	17
Continue Discontinue	Continue my current DMT	23
	Switch to a new DMT	2
	Stay off my DMT	36
	Restart a prior DMT	5
	Restart a new DMT	1
	Total	84

The study procedures will be slightly different for those who are completing Month 24 of the primary trial and simply "rolling over" to extension on the same day, compared to those who already have completed the study. For those rolling over at Month 24, they will be offered participation in the extension trial. If they agree to participate, they will do a second study visit at the Month 24 visit, which concurrently will be Time Zero (T_0) for the extension. This will consist of obtaining informed consent and going through Inclusion/Exclusion criteria. All the data from Month 24 visit will comprise the baseline data for the extension. Current and past DISCOMS study participants will be identified and screened for eligibility. This may include individuals who already have surpassed a full year since last participation in the trial, so long as they continued their original group assignment after the completion of the primary study and for at least for one additional year, or until they had a relapse or new MRI lesion, as determined in screening. These individuals will explicitly be included, upon verification of the defining event. Patients will be approached at their next study visit or by phone (if they've already completed the original study) by the PI and/or a study coordinator about participating in the study. The local PI for the study will verify accuracy of meeting inclusion criteria, and screening and consent may take place in person or by electronic means. Participants must agree to have a single SOC, month 36 MRI done by their primary neurologist and have the results and the MRI disk sent to the study site, to be assessed by a blinded central reader as has been done during the primary trial. All research visits will be conducted at the same time as SOC visits when possible, or as separate visits if not possible or the patient receives SOC elsewhere. For those who have exceeded 30 months from onset in the primary trial, the P_1 visit (a telephone call) will not occur. All patients will undergo the T_1 visit at 36 months, or longer should they have already exceeded 36 months from onset of their participation in the primary trial.

Please see Table 2 below for the schedule of study activities.

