All participants will undergo the T_1 visit, which will include a formal, blinded relapse assessment by the Examining Physician (EDSS rater) in conjunction with the PI (see section E). Prior to enrollment, the enrolling physician will certify, based on their personal review of the prior MRI scans and/or reports which will include data from the 24 month primary DISCOMS trial, that the scans have been stable for a minimum of 4.5 years (review of minimum of two scans, although it could be more, separated by at least 4.5 years). MRI scans at T_1 , 36+ months after onset of participation in the primary trial, will be performed as per usual SOC, paid for by patient insurance, at whatever site is normally used by the patient (preferably the same scanner each time, and preferably the same scanner as the investigation site), and should be done on a MRI machine with magnet 1.5 Tesla or greater, with and without contrast. Gadolinium may be withheld at the discretion of the PI or request of the patient. The window for T_1 MRIs will be 60 day before or 120 days after the T_1 study visit, and will be analyzed by a central, board-certified, blinded neuro-radiologist for new activity compared to prior scans. All MRI scans will be read locally for safety and clinical purposes, and PIs will communicate any significant MS or non-MS findings to the primary neurologist (should they not be the primary neurologist). Any new lesion documented on the T_1 MRI scan will prompt delivery of a notice within 48 hours, to the PI, that the patient has achieved the endpoint of the study, with a description of relevant findings.

In the event of a suspected relapse, the patient will be instructed to contact their physician and the study coordinator at their local site within 48 hours of new symptoms and come in for an unscheduled visit and relapse evaluation within seven days of symptom onset. Use of corticosteroids will be at the discretion of the patient and the local PI or other physician. Use of systemic steroids to treat MS symptoms will be concluded to be a Protocol-defined relapse. As at scheduled visits, the determination of a relapse at an unscheduled visit will be made by the blinded EDSS examiner, who will perform the EDSS and only then receive information about recent clinical history.

D. Risks/Safety:

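### The exclusion list bars anyone given steroids for a relapse after DISCOMS, although the protocol says post-DISCOMS failures are recruited and counted

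*Combined protocol and SAP*

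**What the plan says.** The exclusion criteria in III.B (Description of Population to be Enrolled) contain a list of things that must not "have occurred during the original DISCO MS study or since completing the study". Two entries matter here. The steroid entry ends: "Any use of steroids to treat MS relapse, possible relapse, or pseudo-relapse is excluded". A second entry reads: "Use of alemtuzumab, mitoxantrone, cyclophosphamide, methotrexate, cyclosporine, rituximab, or cladribine".

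The inclusion criteria in the same section address people who completed DISCOMS without an event, but "who have a relapse or scan change AFTER ending participation in DISCOMS but before entering the extension ARE eligible and will be recruited". The reason given is that "we do not wish to undercount new activity that occurs after exiting DISCOMS".

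III.C (Study Design and Research Methods) repeats the rule twice. Of people whose medication assignment changed because of a relapse, new lesion or other MS-related reason between months 24 and 36, it says "These individuals can and should be included" and that they count as failing in the Kaplan-Meier curve. Of people found at screening to have had a relapse or new lesion after DISCOMS, it says: "These individuals will explicitly be included, upon verification of the defining event".

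On the endpoint, III.C states: "Use of systemic steroids to treat MS symptoms will be concluded to be a Protocol-defined relapse". The endpoint definitions in III.D say the same twice more, once adding that it holds whenever the patient was seen.

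**The concern.** For the period between leaving DISCOMS and entering the extension, a steroid-treated relapse is at once a ground for exclusion and a primary-endpoint event that the protocol says it will recruit and count. A site cannot follow both sentences, and sites that choose differently will enrol different people.

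Read literally, the list removes failures before they can be counted, so event rates are biased down. The effect on the arm difference depends on where the losses fall. Equal numbers lost leave the difference about the same but narrow its interval. Loss only among discontinuers moves the result toward meeting the 0.08 margin; loss only among continuers moves it away. Patients know their assignment (II, last paragraph) and so does the treating physician (III.E), so equal loss cannot be assumed.

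Steroid use also matters for ascertainment. Under III.D a relapse not seen within 7 days does not otherwise qualify as protocol-defined, but steroid treatment qualifies it. For people outside study follow-up at the time, the list therefore closes one of the main routes by which a past relapse could count.

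**Working it through.** **1. The texts compared, for an event after DISCOMS exit and before extension entry**

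| Situation | Recruit-and-count rule (III.B inclusion, III.C) | Exclusion list (III.B) |
|---|---|---|
| Relapse treated with steroids | Eligible, counted | Barred |
| Listed agent started because of new MS activity | Eligible, counted | Barred |
| Listed agent used for another reason | Not addressed | Barred; ordinary criterion, no conflict |
| Relapse or lesion, no steroids, no listed agent | Eligible, counted | Not barred by these lines |

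People who roll over at month 24, events after T0, and lesions first found on the T1 MRI are not affected.

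**2. Who is exposed**

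Exposure applies to anyone with a gap between DISCOMS exit and extension entry. III.C gives the position on 15 December 2020: 123 of 260 had completed (123/260 = 47.3%), and 49 of those were 12 or more months out (49/123 = 39.8%). T0 may fall on the same day as T1 (Table 2 footnote), so for some people the whole extension interval precedes entry. These are upper-end counts, taken before screening and before the limit to 10 sites. In Table 1, (17 + 5 + 1)/84 = 27.4% planned to leave their assigned group.

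**3. Effect of one person**

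If the place is refilled by someone event-free, one lost failure lowers the arm's proportion by 1/n. At 50 per arm (III.F, Sample Size) this is 1/50 = 2.0 points, and 2.0/8 = 25% of the margin. At the 59/41 split expected in III.C it is 1/59 = 1.7 points (discontinue) or 1/41 = 2.4 points (continue).

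**4. The plan's own worked figure**

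For 10/50 against 3/50, the one-sided Fisher exact p-value is 0.0357, which reproduces the stated 0.036. With places refilled, losing one discontinue failure (9 v 3) gives 0.061, one continue failure (10 v 2) gives 0.014, and one in each arm (9 v 2) gives 0.026.

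**5. Effect on the margin test, illustration only**

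The documents do not give the number of events lost, so the counts here are assumed. Without censoring, the Kaplan-Meier estimate with Greenwood variance is the Wald interval, with upper 95% bound

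p_D − p_C + 1.96 × √[p_D(1 − p_D)/50 + p_C(1 − p_C)/50].

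For 3/50 in each arm: 0 + 1.96 × √(2 × 0.06 × 0.94/50) = 1.96 × 0.0475 = 9.3 points.

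| Failures counted, discontinue v continue | Wald upper bound | Newcombe upper bound |
|---|---|---|
| 3/50 v 3/50 (none lost) | 9.31 | 10.95 |
| 2/50 v 3/50 (one discontinue lost) | 6.53 | 8.25 |
| 2/50 v 2/50 (one in each lost) | 7.68 | 9.89 |
| 3/50 v 2/50 (one continue lost) | 10.53 | 12.62 |

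Under Wald, losing one discontinue failure, or one in each arm, takes the bound below 8. Under Newcombe no bound falls below 8. At 10/50 v 3/50, losing one discontinue failure moves the Wald bound from 26.9 to 24.5 and leaves the conclusion unchanged.

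**The case against.** The best defence is that the intent can be recovered. Three specific statements in III.B and III.C say these people are included, against one general list. III.B's other unqualified bar, on leaving the assigned treatment, is already understood to yield to the III.C exception, so the steroid line might yield in the same way. It does not follow: that exception is worded for a change of medication assignment and does not mention steroids. A site working from the list would have no ground to set the steroid line aside.

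A second defence is textual. The steroid bullet is garbled at its start, and its last bar could mean that MS-related steroid use is left out of the course count. That does not fit the heading of the list, or the next sentence, which names inhaled and topical steroids for non-MS use as the ones that do not exclude.

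Third, the line also covers pseudo-relapse, which III.D classes as not a relapse. This stands in part: steroid treatment of worsening not attributed to MS is not a failure. But III.D counts any MS-attributed worsening treated with systemic steroids, however it was categorised.

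The criticism of the margin illustration is fair. III.F ties the 0.08 test to the linkage with DISCOMS, which cannot be computed from the documents; III.E concedes that the extension alone lacks power for non-inferiority; and the crossings depend on the assumed counts. At 5/50 v 5/50, losing one discontinue failure moves the Wald bound from 11.8 to 9.2, with no crossing, and 2/50 v 2/50 already starts at 7.7. The case therefore rests on the contradiction and the per-person effect, not on any crossing. Low power is no excuse for it, since III.F makes estimation of the difference the primary goal and missing failures bias that estimate.

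**Conclusion.** The concern holds: the eligibility text is wrong as written and should be fixed. This is an internal contradiction, not a dispute with the design. It is firm for steroids. For the seven agents it is conditional on use having followed post-DISCOMS MS activity. For activity-driven changes of DMT in general, III.C already makes an exception and III.B lacks only a cross-reference.

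The overall size and direction are unknown, and the documents do not show that anyone was turned away on these grounds. What can be stated is the effect per person: 2.0 points of an arm's event proportion at 50 per arm, or 1.7 to 2.4 at a 59/41 split, assuming the place is refilled by someone event-free. With few events, one or two people could matter to the result; at the plan's 10 v 3 example the margin conclusion would not change.

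**What to change.** Reconcile the exclusion list with the recruit-and-count rule:

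- For eligibility, limit the steroid line to the DISCOMS period, and do the same for the agent line where use followed new MS activity.
- Count a post-DISCOMS event at its own date if it meets the endpoint definition.
- Add a cross-reference in III.B to the III.C exception for activity-driven DMT changes.
- Recheck screening records for anyone rejected on these grounds and report the number by arm.

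If the sponsor means the bar to stand after DISCOMS, the inclusion criterion and both statements in III.C must say so, and the number barred in each arm should appear beside the primary result. Either way, this settles who is counted, not how anyone is treated.

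The cost is a short amendment and a one-off check, with no extra visits or staff; this assumes sites kept usable screening records, which the protocol does not describe. The drawback is that some participants will have had post-event therapy that could affect EDSS and patient-reported outcomes at T1. Flag them and show Aims 2 and 3 with and without them. Time to first event is unaffected, and III.D already accepts the same situation for events after entry by keeping those participants in follow-up.
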